2.2 Study Disease; Breast Radiation Treatment & Toxicities

Radiation therapy for locally advanced breast cancer has been well established to provide local control and, in some studies, has been shown to provide a survival benefit.¹⁷⁻²⁰ Conventional treatment delivers radiation to the breast/chest wall and draining lymphatics. This increases the complexity of treatment planning. Depending on patient anatomy, it is often technically difficult or impossible to provide homogeneous coverage of the target volume while producing acceptable doses to the heart and lung and it is often necessary to compromise coverage of target volumes in order to avoid toxicity. This is particularly problematic for patients who have undergone breast reconstruction. The rationale for the use of proton radiation for the treatment of breast cancer is to provide adequate coverage of target volumes and to decrease late toxicity by reducing the dose delivered to normal tissues and to allow for patients with breast reconstruction to proceed to radiation without the need for additional procedures to improve anatomy for radiation.

Estimating the risk of late complications for this group of patients is difficult. The latency between radiation treatment and the appearance of long-term side effects is high and therefore lengthy follow-up is necessary to gather adequate data and draw meaningful conclusions. Although many reports of late complications exist, these data are generally from studies utilizing dated techniques. Modern radiation delivery may lower the occurrence of late side effects, but it is too early to perform adequate assessments. We must assume a risk, even with current radiation treatment, and strive to decrease the amount of radiation delivered to areas and organs known to result in late toxicities for breast cancer patients in the past. In addition, new chemotherapeutic agents increase the risks of certain toxicities, thus making the avoidance of radiation dose to the heart and lung more critical.

Earlier radiation trials reported an increase in morbidity and mortality due to cardiac disease, predominantly in patients treated for left sided breast cancer.^{15, 21-22} Some authors even suggest that increased mortality from ischemic heart disease was the reason for the absence of a survival benefit for patients treated in the earlier post-mastectomy radiation trials.²³⁻²⁴ More recent post-mastectomy studies utilizing modern techniques and fractionation schedules have demonstrated survival benefits and no increase in cardiac mortality to date.²⁵⁻²⁶ After computed tomography (CT)-based radiation treatment planning was developed, the relationship between radiation dose, volume of heart irradiated, and cardiac outcomes could be more closely evaluated. It has generally been established that the risk of cardiovascular disease increases with increasing mean heart dose. Doses in excess of 30 to 40 Gy to small volumes of the heart are felt by some authors to increase a patient's risk of cardiovascular disease and may lead to increased

CONFIDENTIAL

This document is confidential. Do not disclose or use except as authorized.

cardiac events.²⁷ Doses of 25 Gy have been shown to induce temporary perfusion defects and ≥ 5 -6% of the heart receiving ≥ 25 -27 Gy has been accepted by some to define “unfavorable cardiac anatomy” based on correlation of this heart volume to the Stockholm trial for patients with left sided tumors that showed a high rate of cardiac morbidity and mortality.^{15, 21-22, 28-29} There is emerging data that doses to specific parts of the heart, such as the coronary arteries, may be more important in predicting cardiac outcomes.³⁰ Strain echocardiogram has recently shown promise as an accurate and relatively inexpensive study to determine myocardial abnormalities in the left ventricle for doses > 3 Gy immediately post radiation and at 2 months following radiation.³¹ Control patients receiving right sided radiation did not show any changes on post radiation studies. Pericarditis is a very rare toxicity, occurring in $<1\%$ of patients, but may lead to hospitalization.³² In addition, the increased use of cardiotoxic chemotherapy over the past several years adds yet another confounding factor to determining the effect of radiation therapy on cardiac outcomes. Doxorubicin and Herceptin, particularly when used in combination, are known to increase the risk of cardiac disease.³³⁻³⁴ These agents were not included in the chemotherapeutic regimens used in the aforementioned trials. Currently, Doxorubicin and Herceptin are both included in standard chemotherapeutic regimens and are often administered in combination.³⁵ It is not fully known how radiation therapy in the setting of these agents will affect cardiovascular outcomes. Maximal cardiac sparing achieved through proton therapy has the potential to decrease this risk by decreasing mean heart dose as well as volume receiving 40 Gy and 25 Gy (Figure 2 & 3).

Symptomatic radiation pneumonitis is a sub-acute side effect of radiation for treatments involving lung tissue.³⁶ When irradiating the chest wall and regional lymphatics, 20-30% ipsilateral lung may receive radiation to a dose of 20 Gy. With implants in place, this dose may be even higher and this is one reason why it may be recommended that implants be removed or reconstruction be delayed. In addition, recent literature for patients being treated for lung cancer report the importance of large volumes of lung receive low dose irradiation (5 Gy or 10 Gy).¹² Although the meaning of this for patients with breast cancer is less clear, it is important to note the techniques using electron radiation and/or some IMRT techniques generally decrease the volume of lung receiving 20 Gy, but increase the volume of lung receiving lower doses of radiation. Protons are capable of reducing both high and low doses of radiation to the lung. (Figure 3). Radiation pneumonitis is reported in approximately 1-5% of patients treated for breast cancer without concurrent chemotherapy.^{33, 37-38} However, the risk of radiation pneumonitis has been shown to increase with treatment of the regional lymph nodes and/or concurrent chemotherapy and rates as high as 20% have been reported in patients treated with concurrent paclitaxel and radiation.³⁹⁻⁴¹ Radiation pneumonitis generally resolves without treatment, but may require hospitalization or a course of steroids. The incidence of RP as reported by several recent series that utilized both modern chemotherapy and radiation therapy techniques are summarized below. The majority of these reports have used the Radiation Therapy Oncology Group (RTOG) acute lung morbidity scoring system to describe the severity of RP:

CONFIDENTIAL

This document is confidential. Do not disclose or use except as authorized.

	Grade 0	Grade 1	Grade 2	Grade 3	Grade 4	Grade 5
RTOG ACUTE LUNG MORBIDITY SCORING CRITERIA	No Change	Mild symptoms of dry cough or dyspnea on exertion	Persistent cough requiring narcotic, antitussive agents/dyspnea with minimal exertion	Severe cough, no response to narcotic antitussives or dyspnea at rest/clinical or radiological evidence of acute pneumonitis/intermittent O ₂ or steroids may be required	Respiratory insufficiency/continuous oxygen or assisted ventilation	Fatal

The following retrospective studies report on incidences of RP after adjuvant radiation for breast cancer. It is important to note that only two of the series included patients who required internal mammary lymph nodes.^{37, 39} Voduc reported a 2% incidence of grade 2-3 RP using the RTOG scale in a group of 77 women with breast cancer treated at the British Columbia Cancer Agency (BCCA). No grade 4 or 5 events occurred. All patients had lymph node–positive disease with negative estrogen receptor expression and underwent surgery, adjuvant doxorubicin/cyclophosphamide for four cycles followed by four cycles of paclitaxel (AC,T) followed by radiation therapy. This study represents a patient population who were treated with the systemic regimen that most of these patients in the proposed study will receive. Yu and Buchholz reported the MD Anderson Cancer Center (MDACC) incidence of RP in a Phase III study comparing neoadjuvant four cycles of paclitaxel followed by four cycles of 5-fluorouracil, doxorubicin, cyclophosphamide (FAC) versus eight cycles of FAC.³³ Of 524 patients treated in the study, 189 also received radiation therapy. RP was scored using the RTOG scale. Clinically evident pneumonitis was observed in 5% of the paclitaxel-FAC group and 4.5% of the FAC-only group (difference not significant). Only two patients of 189 required steroids, one other required narcotics, and none were hospitalized. Taghian et al. from the Massachusetts General Hospital (MGH) reported RP rates in 41 breast cancer patients treated with mastectomy and axillary lymph node dissection followed by four cycles of adjuvant doxorubicin/cyclophosphamide followed by four cycles of paclitaxel.³⁹ Radiation therapy to the chest wall and regional lymphatics was given concurrently with paclitaxel in 21 patients and sequentially in the remainder. In contrast to the BCCA and MDACC experiences, an incidence of 14.6% (6 of 41 patients) grade 2-3 RP using the RTOG scale was observed at the MGH regardless of the sequencing. Five of the events were grade 3 and no grade 4-5 events occurred. Lind et al reviewed Duke’s experience with RP in a cohort of breast cancer patients treated with breast-only radiation therapy versus comprehensive radiation therapy.³⁷ In 319 patients who received radiation to the breast alone the RP rate was 0.9%. When comprehensive radiation therapy was employed, the RP incidence increased to 4.1% (12 of 294 patients). All 12 patients were

CONFIDENTIAL

This document is confidential. Do not disclose or use except as authorized.

treated with oral corticosteroids. There were neither hospitalizations nor deaths from pneumonitis, which means that the incidence of 4.1% may be regarded as the incidence of RTOG grade 3 events. The Duke report predated the widespread use of taxane chemotherapy, but AC chemotherapy or cyclophosphamide, methotrexate, and 5-fluorouracil was given to 42% of the group, which resulted in a RP rate of 3.8%. Beal and McCormick reported a small series of 38 node-positive breast cancer patients treated with surgery, adjuvant (AC, T), followed by comprehensive radiation therapy at MSKCC.³⁸ No cases of RP were seen in this group after a median follow-up of 28 months. However, none of the patients in this study required irradiation of the internal mammary lymph nodes.

CONFIDENTIAL

This document is confidential. Do not disclose or use except as authorized.

Summary of Retrospective Studies Reporting RP After Breast RT:					
Author	Institution	Publication Year	n	Overall RP Reported (RTOG Grade)	Subset with RTOG Grade 3
Taghian	MGH	2001	41	14.6% grade 2-3	12%
Lind	Duke	2002	294	4.1% grade 3	4.1%
Voduc	British Columbia	2004	77	2% grade 2-3	2%
Yu	MDAH	2004	189	5% grade 2-3	1%
Beal	MSKCC	2005	38	0%	0%

In order to assess the feasibility endpoint in the proposed study, we are most interested in capturing incidences of RP that requires corticosteroids or hospitalization (RTOG grade 3-5). However, no series reported any fatalities or grade 4 events from RP after breast RT, so serious pneumonitis in this population appears to be limited to RTOG grade 3 events. The weighted average for grade 3 RP in these series using the RTOG scale is around 3.3%. Again, not all of the reported series included patients who required internal mammary lymph node radiation.

The National Cancer Institute (NCI) has advocated use of the CTCAE in clinical trials. Relevant sections from the CTCAE version 4 are available in Appendix 1. Therefore, in capturing treatment-related pulmonary toxicities secondary to our proposed treatment, we will use the CTCAE adverse events scale listed above. CTCAE toxicities >3 appear to correspond to the level of treatment-related pulmonary events that we are interested in using for the infeasibility end point and correspond most closely with grade 3-5 toxicities on the old RTOG scale. For the feasibility endpoint, we will score all cases of pneumonitis, but are most interested in those treatment-related pulmonary toxicity events that are greater than or equal to grade 3. Although we will score the level of toxicity over time for all patients, for purposes of determining infeasibility, we are only interested in the number of patients who experience grade 3-5 pulmonary toxicity. A given patient either has or does not have such an event, in which case she will be scored as a failure for this endpoint if present.

CONFIDENTIAL

This document is confidential. Do not disclose or use except as authorized.

There is limited data on second malignancy following the treatment of breast cancer, but available studies do indicate an increased risk.⁴² Radiation-induced sarcomas have been reported with rates ranging between 0.2 to 0.48 percent at 10 to 15 years.⁴³⁻⁴⁴ Increased rates of lung cancer and squamous cell carcinoma of the esophagus have also been reported.^{42, 45-48} Although the risk of a radiation induced malignancy is relatively small, considering the large number of patients treated and the gravity of a second malignancy, it cannot be ignored. Young patients are at particularly high risk of second malignancy.

Breast reconstruction is considered an integral part of treatment for breast cancer and should be discussed and offered to women undergoing mastectomy. For patients undergoing mastectomy, reconstruction offers benefits of improved psychosocial well being and body image⁴⁹. Many different types of reconstruction are available, but they can be categorized into 2 major groups; 1) prosthetic implants, including saline or silicone implants that can be placed in a one step procedure or with an expander placed at the time of mastectomy and permanent implant placed during a separate surgical procedure and 2) autologous implants using the patient's own tissue. What type of reconstruction is chosen depends on several factors including patient anatomy, comorbidities, need for radiation, and patient preference. The decision to proceed with immediate or delayed reconstruction also depends on several factors, including radiation. Benefits to immediate reconstruction include the need for only one surgical procedure, psychological benefits, and cost. The potential disadvantages include the negative impact on radiation planning⁵⁰⁻⁵². Some radiation oncologists recommend that reconstruction always be delayed for patients receiving radiation therapy due to interference with radiation delivery with standard photon and electron techniques.⁵⁰ In addition, many centers have seen an increase in the rate of contralateral prophylactic mastectomy and these cases create a particular challenge for radiation planning.⁵³⁻⁵⁴ The properties of protons will allow for radiation therapy for these patients without compromise of treatment plan or need for additional procedures to reduce the size of the implant or remove the implant (Figure 4 &5). Protons are delivered en face similar to electrons, but have the ability to treat to greater depths and with less scatter. Electrons can be used to treat the chest wall superficially in cases without an implant in place, but they cannot treat to a sufficient depth to reach the chest wall beneath an implant. Photons may be used, but it is often difficult to use optimal angles, particularly when bilateral implants are in place. Immediate breast reconstruction has advantages of providing greater psychosocial benefits compared with delayed reconstruction by allowing patients to awake from surgery with at least a partially reconstructed breast in place. This has been shown to provide patients with improved body image and self esteem and less anxiety, depression, and impairment of sexual attractiveness. Immediate reconstruction has also been shown to provide better esthetic results and often allows for more options for the type of reconstruction and is less costly than delayed reconstruction. Some studies indicate that pedicled transverse rectus abdominis myocutaneous flap (TRAM) tolerate postmastectomy RT very well and delivery of radiation may be less technically challenging with TRAM reconstruction compared to prosthetic reconstruction.^{50, 55-57}. Prosthetic based implants are also feasible in the setting of postmastectomy RT. While some studies report feasibility and outcomes with permanent implant placement prior to

CONFIDENTIAL

This document is confidential. Do not disclose or use except as authorized.

radiation, many advocate for placement of a tissue expander at the time of mastectomy and exchange of the expander for permanent implant following radiation to allow for manipulation of expander for radiation if needed. Others advocate that exchange of the implant prior to radiation will result in a decreased rate of complications because of the avoidance of performing an operation in an already irradiation field (Ho, A, abstract ASTRO 2010).⁵⁸ In any case, many women undergo immediate reconstruction due to preference or because the need for radiation is not known at the time of surgery. Proton radiation will allow for these patients to avoid additional procedures necessary to deliver radiation and potentially improve quality of life and cosmetic outcome as a result. Because the dose delivery is more homogeneous with protons, there may also be a benefit in cosmesis due to decreased “hot spots”.

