1.2 Primary Objectives

1.2.1 To determine the feasibility of using proton radiation for the treatment of invasive breast cancer following surgery (mastectomy or breast-conserving) based on the occurrence of grade 3 or higher radiation pneumonitis or any grade 4 toxicity within 3 months after the completion of radiation treatment. The goal is to enable women with breast reconstruction to undergo radiation therapy without removal or manipulation of reconstruction in order to allow radiation delivery without excessive pulmonary and cardiac dose and to enable patients with unfavorable cardiac anatomy (as defined by $\geq 5\%$ of the heart receives ≥ 20 Gy and/or LAD receives ≥ 20 Gy with conventional planning) to undergo chest wall irradiation with better cardiac sparing.

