1.3 Secondary Objectives

1.3.1 The endpoints in these objectives are descriptive and will form the basis for designing future studies. The Common Terminology Criteria for Adverse Events (CTCAE) version 4 will be used for grading toxicities.

- To evaluate the rate and severity of acute skin toxicity
- To evaluate the rate and severity of radiation pneumonitis, a sub-acute toxicity
- To evaluate the rate and severity of late skin toxicity
- To evaluate cosmetic outcome and patient satisfaction with cosmetic outcome

CONFIDENTIAL

This document is confidential. Do not disclose or use except as authorized.

- To evaluate acute and late toxicity of breast reconstruction following proton radiation
- To evaluate the need for unplanned additional surgery for breast reconstruction
- To evaluate early signs of cardiac effects from radiation therapy using Strain Echocardiogram

1.3.2 To describe the 5 year progression free survival rate of patients with breast cancer treated with proton radiation.

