12.1 Study Design/Endpoints

This is a pilot study substituting proton radiation for photon radiation, seeking to show the feasibility of proton radiation and to assess the rate of acute, sub-acute and late toxicities during and after proton radiation to the left chest wall and regional lymphatics. It is anticipated that patients undergoing proton radiation will not have increased toxicity compared to patients who have historically undergone photon radiation.

Proton radiation will be considered to be feasible as adjuvant treatment for invasive breast carcinoma in each cohort following surgery if the rate of grade 3 or higher radiation pneumonitis within 3 months of treatment were no more than 5%, within the range associated with conventional techniques of adjuvant radiation. In addition to radiation pneumonitis, the feasibility of proton radiation will also be compromised by any grade 4 effect occurring within 3 months of treatment, as well as skin toxicity and pericarditis. If 2 or more of the initial 12

CONFIDENTIAL

This document is confidential. Do not disclose or use except as authorized.

patients were to experience grade 3 or higher radiation pneumonitis or any grade 4 toxicity within 3 months of finishing radiation, accrual to a cohort will not continue further. The probability of stopping early is only 12% if the underlying rate of grade 3 or higher radiation pneumonitis or any grade 4 toxicity were truly 5%. Otherwise, the cohort will proceed to enroll a total of 26 patients and declare the feasibility of proton radiation if no more than 2 of them were to experience grade 3 or higher radiation pneumonitis or any grade 4 toxicity within 3 months after treatment. The two-stage design provides 81% power to accept that proton radiation is associated with a 5% rate of grade 3 or higher radiation pneumonitis or any grade 4 toxicity in a treated cohort. However, the probability is only 20% for declaring the feasibility of proton radiation if the underlying rate grade 3 or higher radiation pneumonitis or any grade 4 toxicity were truly 15%.

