Dysphagia	Dysphagia	Symptomatic, able to eat regular diet	Symptomatic and altered eating/swallowing (e.g. altered dietary habits, oral supplements); IV fluids indicated <24 hrs	Symptomatic and severely altered eating/swallowing (e.g., inadequate oral caloric or fluid intake); IV fluids, tube feedings, or TPN indicated ≥24 hrs	Life-threatening consequences (e.g., obstruction, perforation)	Death
Fibrosis-deep connective tissue	Fibrosis-deep connective tissue	Increased density, "spongy" feel	Increased density with firmness or tethering	Increased density with fixation of tissue; operative intervention indicated; interfering with ADL	Life-threatening; disabling; loss of limb; interfering with vital organ function	Death
Pneumonitis/Pulmonary Infiltrates	Pneumonitis	Asymptomatic, radiographic findings only	Symptomatic, not interfering with ADL	Symptomatic, interfering with ADL; O2 indicated	Life-threatening; ventilatory support indicated	Death
Dyspnea (Shortness of Breath)	Dyspnea	Dyspnea on exertion, but can walk 1 flight of stairs without stopping	Dyspnea on exertion but unable to walk 1 flight of stairs or 1 city block (0.1 km) without stopping	Dyspnea with ADL	Dyspnea at rest; intubation/ventilator indicated	Death
Hypoxia	Hypoxia	--	Decreased O2 saturation with exercise (e.g. pulse oximeter <88%); intermittent supplemental oxygen	Decreased O2 saturation at rest, continuous oxygen indicated	Life-threatening; intubation or ventilation indicated	Death
Cough	Cough	Symptomatic, non-narcotic medication only indicated	Symptomatic and narcotic medication indicated	Symptomatic and significantly interfering with sleep or ADL	--	--
FEV1	FEV1	90-75% of predicted value	<75-50% of predicted value	<50-25% of predicted value	<25% of predicted value	Death

CONFIDENTIAL

This document is confidential. Do not disclose or use except as authorized.

Pulmonary Fibrosis (radiographic changes)	Pulmonary fibrosis	Minimal radiographic findings (or patchy or bi- basilar changes) with estimated radiographic proportion of total lung volume that is fibrotic of < 25%	Patchy or bi-basilar changes with estimated radiographic proportion of total lung volume that is fibrotic of 25 - <50%	Dense or widespread infiltrates/consolidation with estimated radiographic proportion of total lung volume that is fibrotic of 50 - <75%	Estimated radiographic proportion of total lung volume that is fibrotic is ≥75%; honeycombing	Death
--	-------------------------------	--	--	---	--	--------------

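### The conventional pneumonitis rates are RTOG grade 3, which steroid treatment can define; the trial counts CTCAE grade 3 or higher, which in the protocol's table it cannot, so the comparison is not like-for-like

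*Combined protocol and SAP*

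**What the plan says.** Section 1.2.1 defines the primary event as "grade 3 or higher radiation pneumonitis or any grade 4 toxicity within 3 months after the completion of radiation treatment". Section 1.3.1 fixes the scale: "The Common Terminology Criteria for Adverse Events (CTCAE) version 4 will be used for grading toxicities". Section 12.1 calls a cohort feasible if the rate of grade 3 or higher pneumonitis "were no more than 5%, within the range associated with conventional techniques of adjuvant radiation".

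The evidence on conventional techniques is in Section 2.2. It names the target: "we are most interested in capturing incidences of RP that requires corticosteroids or hospitalization (RTOG grade 3-5"). The RTOG table printed there includes "steroids may be required" among the grade 3 descriptors. The largest series is classed as grade 3 because all 12 affected patients had oral corticosteroids and none was hospitalized or died, "which means that the incidence of 4.1% may be regarded as the incidence of RTOG grade 3 events".

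Section 2.2 then moves to CTCAE and says "CTCAE toxicities >3 appear to correspond to the level of treatment-related pulmonary events that we are interested in using for the infeasibility end point". The CTCAE table in Section 15 (after the performance status scales in Appendix A) gives pneumonitis grade 3 as "Symptomatic, interfering with ADL; O2 indicated". Grade 2 is symptomatic disease that leaves ADL intact. Neither grade mentions steroids or hospitalization.

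**The concern.** The protocol names the event it wants, documents conventional rates for that event, and then counts a different one. Pneumonitis treated with steroids in a patient who keeps ADL and needs no oxygen is in the stated target and in the historical rates. On the printed CTCAE row it is grade 2 and stays out of the feasibility count.

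At stake is the statement that protons fall within the conventional range, which needs the same event on both sides. The rule also tolerates few events (stop at 2 of 12, feasible at no more than 2 of 26), so one reclassified patient can change a cohort's result.

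**Working it through.** **1. Benchmark.** Inputs are the five series in the text and summary table of Section 2.2.

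| Series | RTOG grade 3 events | n | How the text describes them |
|---|---|---|---|
| MGH, 2001 | 5 | 41 | grade 3; treatment not described |
| Duke, 2002 | 12 | 294 | all on oral steroids, none hospitalized |
| British Columbia, 2004 | about 2 (2% of 77 = 1.54) | 77 | treatment not described |
| MD Anderson, 2004 | 2 | 189 | required steroids, none hospitalized |
| MSKCC, 2005 | 0 | 38 | no cases |

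(5 + 12 + 2 + 2 + 0)/639 = 21/639 = 3.29%, which reproduces the stated figure of around 3.3%. The table's rounded percentages give (4.92 + 12.05 + 1.54 + 1.89 + 0)/639 = 20.4/639 = 3.19%.

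Events described by steroid use without hospitalization: 12 + 2 = 14, and 14/21 = two thirds. If none of the 14 met CTCAE grade 3, 7/639 = 1.1% would remain. If all did, the figure stays at 3.3%. The documents do not report ADL or oxygen status for these patients. Events that only CTCAE would count are left out of both figures.

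**2. Design figures.** Let P_k be the binomial probability of k events in the first 12 patients and Q_k the same for the next 14. Under the Section 12.1 rule:

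P(feasible) = P_0(Q_0 + Q_1 + Q_2) + P_1(Q_0 + Q_1).

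- At 5%: 0.5404 × 0.9699 + 0.3413 × 0.8470 = 0.813 (stated 81%). Early stop: 1 − 0.5404 − 0.3413 = 0.118 (stated 12%).
- At 15%: 0.1422 × 0.6479 + 0.3012 × 0.3567 = 0.200 (stated 20%).

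Section 6.3 allows 3 of 26 instead of 2. That gives 87% and 32%, so only the Section 12.1 rule matches the stated figures. The two sections need reconciling, but that is a separate matter; the Section 12.1 rule is used below.

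**3. Effect of the change of scale.** Let f be the share of RTOG grade 3 or higher pneumonitis that also reaches CTCAE grade 3. The documents give no value, so f is an assumption shown over a range. With a true RTOG rate of 15%, the counted rate is 0.15f for pneumonitis alone. Adding an assumed independent 5% rate of other grade 4 toxicity, it is 1 − (1 − 0.15f)(0.95).

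| f | Counted rate, pneumonitis only | Declared feasible | Counted rate with 5% other grade 4 | Declared feasible |
|---|---|---|---|---|
| 1 | 15.0% | 20% | 19.3% | 8% |
| 0.75 | 11.3% | 38% | 15.7% | 18% |
| 0.5 | 7.5% | 63% | 12.1% | 33% |
| 1/3 | 5.0% | 81% | 9.8% | 47% |

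The row f = 1/3 corresponds to none of the 14 steroid-described events reaching CTCAE grade 3 and the other 7 all doing so (7/21). It is a boundary scenario, not an estimate.

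**The case against.** - **The origin of 5%.** A reader might infer that the bar was derived from the RTOG series. The documents do not say so. Section 12.1 only places 5% within the conventional range, and Section 2.2 separately cites pneumonitis in about 1-5% of patients without limiting it to grade 3. This stands. The only grade 3 rates shown are nevertheless RTOG, so they are what the plan offers for judging the range.
- **Direction.** A reader might infer that CTCAE grade 3 is simply the narrower event and that bias toward protons is shown. The scales are not nested. RTOG grade 2 includes dyspnea on minimal exertion, which could interfere with ADL and count under CTCAE. RTOG grade 3 severe cough or dyspnea at rest would probably be CTCAE grade 3 as well. The net direction is therefore likely, not proven.
- **The composite.** The 5% and 15% design rates apply to pneumonitis or any grade 4 toxicity, which broadens the count. With 5% other grade 4 toxicity and f = 0.75, acceptance is 18%, below the nominal 20%. This stands as a limit on size, but it does not bring back the omitted steroid-treated cases: in that column acceptance still rises from 8% to 47% as f falls.
- **Already handled.** Section 2.2 discloses the change of scale, gives a reason (the NCI advocates CTCAE) and hedges its wording. Radiation-related events of grade 2 and above are collected (Section 6), and pneumonitis severity is a secondary objective with exact intervals. The cases are therefore recorded. But the protocol does not call for RTOG grade or for identifying which cases needed steroids, so the reported rates still could not be compared with the benchmark.
- **The symbol >3** in Section 2.2 is probably a slip. The same paragraph later says grade 3 or above, and Sections 1.2.1, 6.3 and 12.1 all say grade 3 or higher.

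**Conclusion.** The point holds as a problem of comparability. The protocol's stated target and its historical rates include steroid-requiring pneumonitis, while its decision count turns on ADL or oxygen. The link between them is asserted without data and does not fit the protocol's own two tables. A finding that protons are within the conventional range would not be like-for-like and would probably flatter protons.

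The size is conditional. For a true 15% RTOG rate, the chance of declaring feasibility runs from 20% to 81% over f = 1 to 1/3 for pneumonitis alone, and from 8% to 47% with an assumed independent 5% of other grade 4 toxicity. Both f and the 5% are assumptions.

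It would be tempting to quote 81% as the design's real error rate, or 1.1% as the true conventional rate. The documents support neither: both require that no steroid-treated patient in the two series had ADL interference or needed oxygen, which is not reported.

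**What to change.** 1. Keep the CTCAE composite as the go/no-go count in Sections 1.2.1, 6.3 and 12.1. Redefining the event as CTCAE grade 3 or steroids or hospitalization would be wider than the RTOG benchmark, would tie the primary event to open-label prescribing, and would change a primary endpoint after accrual began (August 2011, Section 12.1.1).
2. Add three items to the toxicity form for every pneumonitis case: RTOG grade, steroid use for pneumonitis, and hospitalization for pneumonitis.
3. In Section 12, report for each cohort the rate of RTOG grade 3 or higher (steroid- or hospitalization-requiring) pneumonitis with an exact 95% confidence interval. Base any statement about the conventional range on that rate.
4. In Section 2.2, replace >3 with *grade 3 or higher*, and state that the correspondence of the scales is assumed.

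The cost is a few form fields, plus completing them from records for patients already treated. The statement about the conventional range may become slightly less favourable. The sample size and decision rule do not change.
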